10.3 Protocol deviations

Major protocol deviations will be summarized, overall and by site, based on the SAF and will be grouped into different categories such as:

- Violation of inclusion/exclusion criteria.
- Time schedule deviations.
- Non-compliance regarding intake of IMP/rescue medication.
- Inappropriate intake of concomitant medication.
- Missing essential data.
- Subject not discontinued as per protocol.
- Other non-compliance.

Major protocol deviations will be presented in a subject data listing sorted by site and treatment.

11 DEMOGRAPHICS AND OTHER BASELINE CHARACTERISTICS

No statistical tests for comparison of demographic and baseline data between treatment arms will be performed.

Subject demographics and baseline characteristics will be summarized descriptively as described in Section 8.1. For Part 1 and Observation Period Part 2, in addition to the presentation by the arms as specified in Section 8.1, descriptive summaries will also be presented overall.

Subject demographics will also be presented for the enrolled set (Part 1); presentation will be without treatment group but only for overall.

Furthermore, the subgroups as given in Table 4 will be displayed for subject demographics and other baseline characteristics, excluding medical history and prior and concomitant medication. Details on the programming aspects regarding demographics and other baseline characteristics can be found in Section 18.1.4.

11.1 Subject demographics

Subjects demographics are age [years], body mass index (BMI) [kg/m²], sex, race, ethnicity and age group. Age groups will be 6-<12 years and 12-<18 years.

Weight and height will be collected several times during the trial and will be analyzed separately as safety parameters. The assessments of height and weight at the Enrollment Visit (Visit 1) will be used for the calculation of the BMI. For completeness, baseline values of height and weight are tabulated with subject demographics as well.

Age will be collected at visit V1, V2 and VE.

- Age at Visit V2 will be used for subject demographics of both parts.

Date of signing the informed consent/assent form will be included in the subject data listings only.

11.2 Other baseline characteristics

For parameters collected on more than one occasion during the trial including baseline, the assessment at Baseline Visit will be presented with assessments collected later on and earlier in the trial and not separately for baseline. These parameters are

- 12-lead Electrocardiogram (ECG).
- Laboratory parameters.
- Vital signs.
- Dip stick urinalysis.
- Modified constipation assessment scale (mCAS).
- Physical examination.

As a parameter of special interest, baseline pain will be reported together with the assessments collected later on and earlier and in addition as baseline characteristics.

Further baseline characteristics to be presented are:

- Pain cause (cancer-related pain, non-cancer-related pain)

- Type of pain (neuropathic, nociceptive/somatic, nociceptive/visceral and all possible combinations)
- Baseline pain intensity, pain cause and type of pain will be summarized descriptively.

The results of urine test for drugs of abuse, will be included in the subject data listings only.

11.3 Subject medical history

The assessment of a disease as prior or concomitant is done by the investigator and will be evaluated as documented on the relevant medical history page of the eCRF.

Medical history will be summarized and sorted alphabetically, separately for prior and concomitant diseases, by primary System Organ Class and Preferred Term coded via MedDRA. The number and percentage of subjects with at least one disease will be displayed for each System Organ Class and Preferred Term.

The underlying diagnosis/reason for the pain leading to enrollment of subjects in the trial will be summarized descriptively by primary System Organ Class and Preferred Term in a separate presentation, coded via MedDRA and sorted alphabetically.

11.4 Prior and concomitant medication or therapy

Therapies will only be displayed in the subject data listings.

Prior and concomitant medication is collected in the eCRF as per enrollment. For the analysis, the following algorithms will be used to define prior and concomitant medication:

Part 1

- Prior is all medication stopped prior to the first dose of IMP, regardless of its start date.
- Concomitant is any medication not stopped before the first dose of IMP, but with start date not after the End of Treatment Visit of the Treatment Period (Visit VE).
- Medication starting after the End of Treatment Visit of the Treatment Period (Visit VE) will not be assigned to Part 1, but Part 2.

Part 2

For all presentations, except displaying prior and concomitant medication for subjects in the Observation Period that have switched from the Tapentadol Period to the Observation Period:

- Prior is all medication stopped prior to or at the End of Treatment Visit of the Treatment Period (Visit VE), regardless of its start date.
- Concomitant is any medication not stopped before or at the End of Treatment Visit of the Treatment Period (Visit VE) and, for subjects discontinuing treatment early in the Tapentadol Period, with start date not after Visit ET.

For presenting prior and concomitant medication for subjects in the Observation Period that have switched from the Tapentadol Period to the Observation Period:

- Prior is all medication stopped prior to or at the Early Termination Visit (Visit ET) regardless of its start date.
- Concomitant is any medication not stopped before or at Visit ET, regardless of its start date.

Medication will be summarized and sorted alphabetically separately for prior and concomitant medication by Anatomical Therapeutic Chemical categories (Level 2: pharmacological or therapeutic subgroup and Level 3: chemical or therapeutic or pharmacological subgroup). For each medication the number of subjects will be displayed. In addition the number of subjects with medication taken during IMP administration for the Treatment and Tapentadol Period (flag definition see Section 18.1.5.5) will be displayed.

Medication or therapy taken during IMP administration for the Treatment Period of Part 1 as well as medication or therapy taken during IMP administration for the Tapentadol Period of Part 2 will be flagged in the subject data listing.

Handling incomplete dates is described in Section 18.1.5.5.

12 EXPOSURE AND COMPLIANCE

12.1 Exposure

IMP intake is assessed in the eDiary as well as the drug accountability page of the eCRF. Unless specified differently, analyses described below will be based on data collected in the eDiary.

Part 1

The daily doses of IMP per kg body weight will be determined for each subject and summarized descriptively for each calendar day of the Treatment Period.

A graphical illustration will illustrate the means and 95% confidence intervals of the daily doses of IMP per kg body weight (Tapentadol equivalents; 1 mg morphine PR is equivalent to 2.5 mg tapentadol PR) of each day separately for the two treatment arms.

The duration of exposure will be summarized descriptively. Duration of exposure of Part 1 is defined as:

Date of last IMP administration in Part 1 – Date of first IMP intake +1

Furthermore, the overall average daily dose per kg body weight will be determined for each subject and summarized descriptively. This analysis will be based on data assessed via drug accountability collected in the eCRF.

Part 2

Exposure to IMP is only assessed during the Tapentadol Period and analyses of exposure of Part 2 will only be presented for the Tapentadol Period.

The average daily doses and modal (i.e., most frequent) doses of IMP per kg body weight will be determined for each four-week interval between two visits (excluding visits M1 and M2) and summarized descriptively per interval. In case of more than one modal dose value for an interval, the average of those will be considered.

For a detailed definition of the time intervals and how to handle subjects terminating the Tapentadol Period in between two scheduled visits, see Section 18.1.6.

A graphical illustration will illustrate the means and 95% confidence intervals of the average daily doses of IMP of each interval for the two arms of differently pretreated subjects.

The duration of exposure will be summarized descriptively. Duration of exposure of Part 2 is defined as

Date of last IMP administration in Part 2 – Date of first IMP intake in Part 2 +1

Furthermore the overall average daily dose per kg body weight will be determined for each subject between visit VE and visit ET/F12M and summarized descriptively. This analysis will be based on data assessed via drug accountability collected in the eCRF.

12.2 Compliance

Compliance to the IMP dose regimen (%) is defined as the amount of IMP actually taken by a subject divided by the expected IMP amount the subject should have taken in the respective period and multiplied by 100. The information will be taken from the drug accountability pages and the “Initial Dose/Dose Adjustment”-pages of the eCRF. An algorithm for the calculation of actual and expected IMP amount is given in Section [18.1.7](#).

Compliance will be presented for both parts separately using the following categories: <80%, 80-<95%, 95-105%, >105-120%, >120%.

For Part 1, in addition to the presentation by treatment arm, descriptive summaries will also be presented overall. For Part 2, compliance will only be presented for the Tapentadol Period.

13 EFFICACY ANALYSES

13.1 Primary endpoint

The primary efficacy endpoint and its analyses only involve Part 1 of the trial.

The primary efficacy endpoint is a binary variable “responder”. A subject is defined as “responder” if both of the following criteria are met:

- Completion of the 14-day Treatment Period. A definition is given in Section [8.2.2](#).
- One of the following calculated from the scheduled pain assessments (“pain right now”) is documented during the last 3 days of treatment in the Treatment Period:
 - Average pain <50 on a VAS for subjects aged 12 years to less than 18 years; or <5 on the FPS-R for subjects aged 6 years to less than 12 years.
 - Average reduction from baseline of pain ≥ 20 on a VAS for subjects aged 12 years to less than 18 years; or ≥ 2 on the FPS-R for subjects aged 6 years to less than 12 years.

Pain assessments during the last 3 days of treatment in the Treatment Period means the last six scheduled pain assessments up to the time point of last IMP intake of the Treatment Period whether these fall across 3 (morning assessment 2 days before last IMP intake until evening assessment at the day of last IMP intake given last IMP taken in the evening) or 4 calendar days (evening assessment 3 days before last IMP intake until morning assessment at the day of last IMP intake given last IMP taken in the morning).

Summary statistics for the primary efficacy endpoint for the FAS and PPS will be provided.

13.1.1 Main analysis

The FAS will be the primary analysis set.

Let p_T, p_C be defined as

p_T : expected value of the responder rate in the tapentadol arm

p_C : expected value of the responder rate in the morphine arm

Let the non-inferiority margin be $\delta = 0.2$.

The primary null hypothesis to be tested in this trial is that treatment with tapentadol is inferior to treatment with morphine, i.e.,

$$H_0: p_T - p_C \leq -\delta$$

The alternative hypothesis is that treatment with tapentadol is non-inferior to treatment with morphine, i.e.,

$$H_1: p_T - p_C > -\delta$$

Maximum-Likelihood estimates \hat{p}_T, \hat{p}_C for p_T, p_C will be obtained fitting a logistic regression model to the response using baseline pain intensity, age group, treatment and underlying pain condition as explanatory variables.

The method introduced by Farrington and Manning (1990) will be used to determine the variance estimator \hat{v}_0 .

Based on \hat{p}_T, \hat{p}_C and the Farrington-Manning variance estimate \hat{v}_0 , the p-value of the Farrington-Manning test regarding non-inferiority and the 80% -confidence interval (CI) of the difference in responder rates will be determined.

Non-inferiority of tapentadol versus morphine will be assigned if the lower bound of the CI exceeds the negative non-inferiority margin $-\delta = -0.2$.

For details on the methods and formulas used, see Section [18.1.8](#).

Handling missing data

The primary efficacy endpoint consists of two parts. Information on the first part, *Completion of the 14-day Treatment Period*, will always be available. However information on the pain assessments during the last 3 days of treatment in the Treatment Period might only be partially available. In this case Multiple Imputation will be used to impute missing values. A detailed description of this method can be found in Section [18.1.8](#).

13.1.2 Sensitivity analysis

The sensitivity analyses will only be performed at the final analysis of Part 1.

1. Different analysis set:

To assess the robustness of the results with respect to heterogeneous compliance to the protocol and protocol violation, the analysis of the primary endpoint will be repeated for the Per Protocol Set.

2. Different completer definition:

To assess the robustness of the results with respect to the definition of the primary efficacy endpoint, the analysis of the primary endpoint will be repeated using the following modifications in the definition of a responder:

- Subjects stopping treatment earlier than 14 days because of no further need for opioid treatment (according to reason for discontinuation given in eCRF) will be classified as treatment responders instead of non-responders.

3. Different imputation method:
To assess the impact of the missing imputation method on the results, the analysis of the primary endpoint will be repeated without imputing missing pain assessments. The average of the available pain assessments will be calculated and used to assign responder status. If no pain value during the last 3 days of treatment in the Treatment Period is present for a subject, that subject will be assigned a non-responder.

4. Different adjustment factors:
To assess the robustness of the results with respect to different explanatory variables in the logistic regression model, the analysis of the primary endpoint will be repeated

- Once discarding baseline pain intensity.
- And once including the IMP dose level during the last 3 days of the Treatment Period as specified in Section 18.1.6.1.

5. Bayesian analysis:
A further sensitivity analysis will be carried out by fitting a Bayesian logistic regression model to compare the proportion of responders under tapentadol PR and morphine PR. The Bayesian Framework allows incorporating prior information gathered on tapentadol in earlier trials in the analysis. Prior information that was obtained from trials in adults will be incorporated into the analysis using a conditional power prior approach (see e.g., Neelon and O’Malley 2010), which allows to down-weight the prior information in the final analysis. A detailed description of this analysis can be found in Section 18.1.8.3.
For this sensitivity analysis, the responder status as derived based on the alternative imputation method described in sensitivity analysis 3. above will be used.

6. Exclusion of CRPS patients:
The main analysis of the primary endpoint will be repeated excluding subjects with CRPS as underlying diagnosis/reason for pain as provided in the eCRF.

13.1.3 Other analysis

Summary statistics for the primary endpoint will be provided for each level of the subgroups defined in Table 4 and for subgroups of subjects with and without a neuropathic pain component (based on information from the Pain Condition page of the eCRF at Visit V1).

Furthermore, as exploratory analyses, for subgroup levels that include at least 5 subjects in each of the two treatment groups, the differences in Maximum Likelihood-estimators between morphine and tapentadol and their 80% confidence intervals obtained by the Farrington Manning method will be provided and illustrated together in one forest plot.

In addition, summary statistics for the primary endpoint per IMP dose level during the last 3 days of treatment in the Treatment Period will be presented.

Based on observed, non-imputed data, the individual criteria considered for the response assessment for the FAS will be summarized descriptively. The following categories will be presented:

- Completion of the 14-day Treatment Period (yes/no).
- Average pain during the last 3 days of treatment in the Treatment Period <50 (VAS) or <5 (FPS-R) (yes/no).
- Average pain reduction for the last 3 days of treatment during the Treatment Period from baseline of ≥20 (VAS) or ≥2 (FPS-R) (yes/no).
- Completion of the 14-day Treatment Period and average pain during the last 3 days of treatment in the Treatment Period <50 (VAS) or <5 (FPS-R).
- Completion of the 14-day Treatment Period and average pain reduction for the last 3 days of treatment during the Treatment Period from baseline of ≥20 (VAS) or ≥2 (FPS-R).
- Completion of the 14-day Treatment Period, but average pain during the last 3 days of treatment in the Treatment Period ≥50 mm (VAS) or ≥5 (FPS-R) and average pain reduction for the last 3 days of treatment during the Treatment Period from baseline <20 mm (VAS) or <2 (FPS-R).

The pain related criteria will be presented using VAS for all subjects, using FPS-R for all subjects and using VAS for subjects 12- <18 years or FPS-R for subjects 6- <12 years.

The analysis of the primary endpoint will also be repeated using the following modifications in the definition of a responder:

- Using VAS for all subjects 6- <18 years old to assess the pain related response criteria (average pain <50 or average reduction from baseline pain ≥20 on a VAS).
- Using FPS-R for all subjects 6- <18 years old to assess the pain related response criteria (average pain <5 or average reduction from baseline pain ≥2 on a FPS-R).

13.2 Secondary endpoint

There is no secondary efficacy endpoint in this trial. For secondary safety endpoints, please see Section 15.1.

13.3 Other endpoints

13.3.1 Pain assessed using a VAS and FPS-R scale

Part 1

The diary values are used for statistical analysis.

Daily average pain values will be calculated for each subject as described in Section 18.1.9. For each day during the Treatment Period these averages and their changes from baseline will be summarized descriptively. In addition, these summary tables will be presented for the subgroups as specified in Table 4.

Graphical presentations over time of the Treatment Period for the determined averages and changes from baseline will be provided (mean and 95% confidence interval), including numbers at the bottom of the plot representing the number of subjects by treatment arm and day.

Additionally, the average change from baseline to the last 3 days of treatment in the Treatment Period (last six scheduled assessments) will be summarized descriptively.

Part 2

For the Tapentadol Period of Part 2, the investigator will document the pain that the subject has at each visit in the eCRF using a paper-based VAS and FPS-R. These eCRF values are used for statistical analysis.

Changes in the VAS and FPS-R at each scheduled time point (including Visit F12M) from baseline and the change from baseline to the last assessed pain value, i.e., the value assessed at either Visit F12M or Visit ET, will be summarized descriptively for the Tapentadol Period of Part 2. In case no baseline pain value from the eCRF is available, the last available pain values from the eDiary of the Treatment Period will be used as baseline. In addition, these summary tables will be presented for the subgroups as specified in [Table 4](#).

13.3.2 Rescue medication

The analyses of rescue medication address only Part 1. Rescue medication is assessed in the eDiary and assessed in the drug accountability page of the eCRF.

Analyses based on eDiary-data:

For each day of the Treatment Period (day 1 until day 16) the two endpoints

- Number of daily doses.
- Total daily dose (mg/kg).

will be summarized descriptively and compared to the mean amount of IMP (morphine equivalent) within the treatment arms of that day. The individual daily amount of IMP will be compared over time to the two endpoints with Pearson's and Spearman's correlation coefficients (see [Section 18.1.9](#) for details).

In addition, descriptive statistics will be presented for the subgroups as specified in [Table 4](#).

The time from first IMP to first rescue medication intake will be summarized using time-to-event methods. The calculation of time to first rescue medication and the censoring algorithm are described in [Section 18.1.9](#).

The percentage of days with rescue medication intake will be summarized descriptively as a categorical variable using the following percentage categories: 0, (0-10), [10-20), [20-30), ..., [90-100), 100. The percentages will be calculated considering the day of the first IMP intake up to the day of the last IMP intake of Part 1 (both included).

Analyses based on eCRF-data:

Based on information in the drug accountability page of the eCRF, the average mean daily dose for each subject, i.e., the cumulative volume difference between Visit V2 and Visit VE divided by the number of days between Visit V2 and Visit VE (both days included), will be analyzed descriptively.

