10.6.3 Documentation

The intake of rescue medication (time and dose [mg]) will be documented by the subject, parent or legal guardian on a daily basis in the diary preferably after each intake of rescue medication in the Treatment Period.

Confidential

Protocol KF5503-66
including Amendment 05Page 59 of 137
DMS version 9.0
27 Jul 2017

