12.8 Compliance

Compliance is the adherence to all trial-related requirements (including treatments), GCP, and applicable regulatory requirements.

Trial site compliance will be ensured by the implementation of a quality system and the performance of a combination of trial site visits, training, monitoring visits, and remote verification by the sponsor of appropriate use of electronic tools by the trial site and subjects. Non-compliance will lead to prompt action by the sponsor to secure compliance, and may result in closure of the trial site and notification of the regulatory authorities and/or relevant IEC or IRB. Acceptable time windows for CRF completion will be described in a separate document.

Subject compliance with regards to IMP intake will be confirmed by the investigator or delegated qualified personnel during trial site visits and phone contacts. Compliance will be checked during regular drug accountability as outlined in Section 10.7. Subjects are considered compliant if they have consumed a minimum of 80% and a maximum of 120% of the scheduled tablet consumption between 2 consecutive trial site visits.

Subject compliance with regards to diary entries will be checked by the investigator or qualified delegated personnel on a regular basis. If subjects do not complete the diary correctly, the investigator or qualified delegated personnel is to contact the subject, or parent(s) or legal guardian(s) to ensure diary completion. A subject is considered to be compliant if a minimum of 80% of all twice daily diary entries are available at the end of treatment.

Monitoring of CRF completion, diary compliance, and compliance with IMP intake by the sponsor will be described in a separate document.

Confidential

Protocol KF5503-66
including Amendment 05Page 84 of 137
DMS version 9.0
27 Jul 2017

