13.2 Subject reported outcomes

Diaries for each subject will be provided to the investigator by the sponsor in electronic format for Treatment Period of Part 1 to document the pain assessments (VAS and FPS-R) and intake of IMP and rescue medication, and for Tapentadol Period of Part 2 to document the intake of IMP. The other questionnaires will be reported on paper throughout the trial. An electronic version of the VAS will be used in the electronic diary (Part 1) and paper version of the VAS will be used in the CRF for the Tapentadol Period (Part 2). The electronic version and the paper version of the VAS are both validated.

Subjects will receive their diaries at the investigator's site and will be instructed on how to use it.

Due to the fact that this is a pediatric trial, the possibility for caregivers to enter data in the diaries is possible and will be recorded with a personal identification of the person who made the entry.

Confidential

Protocol KF5503-66
including Amendment 05Page 85 of 137
DMS version 9.0
27 Jul 2017

The data will be collected using an appropriately validated system. No queries will be issued to the investigator for these data, except for clarification of subject identifiers and any operational issues.

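### The percentage of days with rescue medication is taken over all calendar days on IMP, so days without any diary entry lower it

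*SAP*

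**What the plan says.** SAP 13.3.2 lists the summary under the heading "Analyses based on eDiary-data". It says that "The percentage of days with rescue medication intake will be summarized descriptively as a categorical variable", in bands running from 0 through ten-point steps to 100. The days are fixed in the next sentence: "percentages will be calculated considering the day of the first IMP intake up to the day of the last IMP intake of Part 1". The first and the last day of this window both count.

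Other places bear on how this works out:

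- Protocol 10.6.3 has the subject, parent or guardian record rescue intake "on a daily basis in the diary preferably after each intake of rescue medication".
- SAP 18.1.2.11 takes the first and last IMP intake from the eCRF dispense form, with the eDiary in support. The window therefore generally keeps its length when diary days are missing.
- SAP 18.1.10, the programming section for rescue medication, covers correlations and time to first rescue. It does not mention days without entries.
- SAP 18.1.2.8 keeps missing values as missing, but is written for values at a time point or visit.
- Protocol 12.8 foresees gaps: "A subject is considered to be compliant if a minimum of 80% of all twice daily diary entries are available".
- Protocol 13.2 says of the diary data: "No queries will be issued to the investigator for these data", except for subject identifiers and operational issues.

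**The concern.** The numerator and the denominator come from different sources. A day counts as a rescue day only if the diary shows it. A day counts in the denominator because it lies between two IMP dates, whether or not the diary was opened. A day with no entry therefore acts as a day without rescue, although nothing is known about it.

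The summary has some interpretive weight. The responder definition in SAP 13.1 sets no limit on rescue use, and SAP 18.1.8.3 notes that the adult trial's definition did. Rescue is morphine in both arms. A reader who wants to know whether similar responder rates were reached with similar rescue use will look at the rescue summaries. At stake is an understatement of how often rescue was used.

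**Working it through.** The plan gives no figure for this summary, so there is nothing to reproduce. The check is direct arithmetic.

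**Inputs.** The window is D days, first to last IMP intake inclusive (SAP 13.3.2). Illustrations use D = 14, the planned treatment length. Let t be the true number of rescue days and m the number of diary-free days. The documents give no value for m, so all values below are assumed.

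**Formula as written.** Result = 100 × (days with a recorded rescue intake) / D.

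If diary gaps are independent of rescue use, the expected number of recorded rescue days is t × (D − m)/D. The expected result is then

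100 × (t/D) × (1 − m/D) = true percentage × (1 − share of diary-free days).

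**What share is plausible?** The 80% rule in Protocol 12.8 refers to twice-daily entries, not whole days.

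- Over 14 days there are 28 entries, and 80% of 28 is 22.4. So 23 are needed and 5 may be missing, which is at most 2 whole days: 2/14 = 14.3%.
- Over 15 days there are 30 entries and 24 are needed. The 6 missing entries make at most 3 whole days: 3/15 = 20%.
- If 20% of entries are missed independently, both entries of a day are missing on 0.2 × 0.2 = 4% of days.

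A subject at the 80% limit may thus have roughly 4% diary-free days if misses are scattered, and up to 20% if they pair up on the same days. The FAS (SAP 9.4) has no diary requirement, so subjects below 80% also contribute.

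**Results under the SAP formula.**

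- Daily user, 2 of 14 days missing: 12/14 = 85.7%, band [80-90) instead of 100.
- Rescue on 7 of 14 days (50%), 2 days missing at random: 50 × 12/14 = 42.9%.
- True 40%, 4% diary-free: 40 × 0.96 = 38.4%.
- True 40%, 20% diary-free: 40 × 0.80 = 32%.

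**Results with days that have diary data as denominator.**

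- Daily user, 2 of 14 missing: 12/12 = 100%.
- 7 of 14 days, gaps at random: 50% in expectation.
- 7 of 14 days, both missing days rescue days: 5/12 = 41.7%, against 5/14 = 35.7% under the SAP and a true 50%.
- 7 of 14 days, both missing days rescue-free: 7/12 = 58.3%, against 7/14 = 50% under the SAP, which is then right.
- Rescue on one day only, and that day missing: 0/13 = 0%, the same as 0/14.

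**Which entries should qualify a day?** Suppose rescue is always entered, while scheduled entries are absent on 20% of days at random. With true use of 40%, a denominator that also admits days with only a rescue entry gives 40/(1 − 0.6 × 0.2) = 40/0.88 = 45.5%, an overstatement. If days qualify only by a scheduled pain or IMP entry, and rescue is counted on those days alone, the result is (0.4 × 0.8)/0.8 = 40%.

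**The case against.** The strongest reply is that the SAP nowhere says a missing day is rescue-free. It gives a window, and SAP 18.1.2.8 says that missing stays missing. The first part is right: the effect follows from the stated window and the lack of a rule. But the general rule does not say that an empty day leaves the denominator of a per-subject percentage, and a programmer who follows 13.3.2 literally will keep it.

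A reader might also infer that rescue is unchecked outside the diary. The documents do not support that. Bottles are weighed at dispensing and return (Protocol 10.7), returned amounts are checked and discrepancies verified with the family at Visits V3 and VE, and sites follow up poor diary completion (Protocol 12.8). SAP 13.3.2 already plans a mean daily dose from accountability. These safeguards stand, but a cumulative volume cannot be assigned to days.

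Three further readings go too far:

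- That compliant subjects lose 20%. This needs missed entries to fall in pairs on the same days.
- That a new denominator would correct an inflated 0 band. A numerator of zero stays zero under either denominator.
- That SAP 12.1 has the same fault for IMP doses. It says only that "Unless specified differently, analyses described below will be based on data collected in the eDiary"; it does not code an unrecorded intake as no dose, and overall average dose and compliance rest on eCRF accountability.

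Finally, this is not the protocol's main rescue measure. Protocol 8.1.3 names the number of rescue doses by IMP dose level, and 14.2.6.3 focuses on the mean number of daily doses and the mean total daily dose.

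**Conclusion.** The point holds in a limited form. Followed as written, SAP 13.3.2 understates the percentage of rescue days by the share of diary-free days, provided gaps are independent of rescue use. For a true 40% this means about 38% with 4% diary-free days and 32% with 20%. The actual loss depends on a diary completion rate that the documents do not give. If gaps fall mainly on rescue days, the understatement is larger; if they fall mainly on rescue-free days, it is smaller or absent.

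A reader might infer that the rule would create a false rescue-sparing effect between arms. That needs diary completion to differ by arm. The trial is open-label, so this is possible, but nothing in the documents shows it. With equal gap rates and equal true use, both arms are lowered alike.

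The consequence is confined to one descriptive summary of an other endpoint. The primary non-inferiority test and the sample size are not affected.

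**What to change.** Add a rule to SAP 13.3.2 and 18.1.10:

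- Calculate the percentage over days from first to last IMP intake that have at least one scheduled eDiary entry (pain or IMP), and count rescue on those same days. A rescue entry alone should not qualify a day, so that the denominator does not depend on rescue use.
- Keep the calendar-day version as a sensitivity summary.
- Tabulate diary-free days by arm. This also shows how far the 0 band may include subjects whose rescue days went unrecorded, which the new denominator cannot repair.
- Read the result beside the accountability-based mean daily dose that is already planned.

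The cost is a short change of wording, one changed denominator and one small table, with no new data. Percentages will rest on slightly fewer days, rescue recorded on days without a scheduled entry will appear only in the sensitivity version, and bias remains if diary gaps are related to rescue use.
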